### 4.1. Primary Endpoints

- Safety parameters including adverse events (AEs), laboratory tests, and vital signs
- MTD: the highest dose at which  $\leq 33\%$  of subjects have a dose limiting toxicity (DLT) in a cohort of up to 6 subjects
- Recommended Phase 2 Dose (RP2D)
- Objective response rate (ORR)
- Disease control rate (DCR)
- Time to response (TTR)
- Duration of response (DOR)
- Progression-free survival (PFS)
- Time to progression (TPP)

- Overall survival (OS)

If there are no subjects with response (complete or partial response), TTR and DOR related summaries and listings will not be generated.

## 4.2. Secondary Endpoints

- Plasma concentration-time profile and calculation of pharmacokinetic (PK) parameters including, but not limited to:  $AUC_{inf}$ ,  $AUC_{tau}$ ,  $C_{max}$ ,  $C_{min}$ ,  $T_{max}$ , and  $t_{1/2}$
- ORR and gene alterations in tumor tissue or ctDNA at baseline as measured by next generation sequencing (NGS)

## 4.3. Exploratory Endpoints

- Proof of target engagement and changes in mechanism of action biomarkers between baseline and on treatment with SRA737, including, but not limited to: pSer296 Chk1, pS317 Chk1 and total Chk1
- Proof of target engagement and changes in mechanism of action biomarkers between baseline and on treatment with SRA737, including but not limited to: pS317 Chk1, pS345 Chk1, total Chk1, gammaH2AX and RAD51
- Characteristics such as performance status, prior therapy, indication and other known or potential prognostic or predictive factors
- Association of QT, QTc, blood pressure (BP), heart rate, other ECG intervals with time-matched PK concentrations. Profile of QTc over the dosing interval

## 5. DATA CAPTURE AND PROCESSING

Clinical study data will be captured on electronic case report forms (eCRF) and maintained in a Medidata Rave clinical database. The study data will be stored on the SAS server to facilitate further downstream activities. The study data will be mapped using study data tabulation model (SDTM). Data points used for summaries and analyses will be mapped from SDTM to analysis data model (ADaM).

## 6. ANALYSIS AND REPORTING

### 6.1. Interim Analysis

There will also be 2 planned interim reviews on the accumulating data. These are not formal statistical interims, and the reviews are conducted in part for subject safety. There will be no

adjustment to significance levels for reviews of the accumulating data during the trial. The planned reviews will occur at the following time points:

- At the completion of subject follow-up for the last subject enrolled at the end of the dose escalation
- At the completion of the expansion cohort for each indication.

## 6.2. Final Analysis

The final analysis will be conducted after one of the following conditions is met:

- The trial is terminated early.
- The end of trial, which is defined as the date when the last subject has completed the Safety Follow-up visit or the long-term follow-up visit (whichever is later).

Additional analysis may be conducted for regulatory, publication, or decision making purposes.

## 7. SAMPLE SIZE DETERMINATION

The study will enroll up to 170 subjects in total including an estimated 30–50 subjects during dose escalation and 6 indication-specific expansion cohorts each consisting of approximately 20 prospectively-selected genetically-defined subjects. The sample size for dose escalation is based on assumptions of the likely MTD based on allometric scaling and will depend on the number of dose levels required to establish the MTD and RP2D. The final number of subjects enrolled into the trial will depend on the number of dose levels, the number of subjects who participate in both the Dose Escalation and Cohort Expansion phases, and potentially alternative dose schedules explored. A planned sample size of 20 subjects enrolled in each indication-specific expansion cohort will permit confirmation that the 95% confidence intervals around an observed ORR in each cohort is  $\pm 16\%$ .

## 8. ANALYSIS POPULATIONS

### 8.1. Safety Evaluable Population

Safety evaluable population includes all enrolled subjects who receive at least 1 dose of SRA737. Subjects who received the single dose for PK evaluation but never received study treatment during the treatment phase are also included in this population.

### 8.2. Response Evaluable Population

Response evaluable population includes all enrolled subjects who satisfy all of the following conditions. Two sets of criteria are defined for the 2nd condition and hence two response

evaluable populations will be defined: (a) is the original definition per protocol, used in statistical outputs (unless specified otherwise) and (b) is the alternative definition used in exploratory efficacy analysis as described in the CSR. To differentiate the two definitions in the outputs the population line in the TLFs will be “Response Evaluable Population” for definition (a) and “Response Evaluable Population (Alternative Definition)” for definition (b).

1. Have measurable disease and assessment at baseline (for inclusion in expansion cohorts, subjects also need to meet the appropriate protocol criteria for genetically-defined tumor)
2. Two sets of criteria are defined below (a or b) based on the dosing information
  - a. Received at least 75% of 1 cycle of study medication, OR
  - b. An alternative definition might be used for some exploratory efficacy analysis:  
Received at least 75% of cycle 1 study medication at  $\geq 300$  mg or continued on-study after 2 cycles of treatment at any dose level.
3. Have at least one post-baseline disease assessment OR discontinued treatment due to adverse event or disease progression or death

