9.3 TUMOR RESPONSE

All subjects who have measurable disease, receive at least one cycle of SRA737 and have a baseline plus at least 1 post-baseline assessment of disease will be evaluable for response. Subjects who develop clear evidence of PD without a formal disease assessment and those without a formal disease assessment before study withdrawal will be considered non-responders. Complete responses and PRs are required to be confirmed by a subsequent assessment at least 4 weeks later. Stable Disease (SD) determination requires that the relevant criteria be met at least once, a minimum of 6 weeks after the initial dose of SRA737 is given.

Should rapid tumor progression occur before the completion of 4 weeks of treatment the subject will be classified as having early progression.

Tumor response should be classified as “not evaluable” (NE), only when it is not possible to classify it under another response category, for example, when baseline and/or follow-up assessment is not performed or not performed appropriately.

Expert reviewers appointed by the Sponsor may undertake an independent review of the investigator's assessed objective responses (CR and PR). Any independent reviewer's assessment will also be documented in the final clinical study report along with the assessment made by the investigator. The eCRF will reflect the investigator's opinion.

9.3.1 *RECORDING OF RESPONSE IN THE ECRF*

The applicable overall response category for each visit that includes disease assessment must be recorded in the eCRF.

9.3.2 *OTHER DEFINITIONS OF OUTCOME*

- **Toxic death:** Any death to which drug toxicity is thought to have a major contribution.
- **Early death:** Death during the first 28 days of treatment.

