## 9.2.3. Early Withdrawal and Missing Data

All subjects who withdrew early from the study will be included in the reporting if they meet the definition of the analysis population specified in [Section 8](#), regardless whether they were replaced for the purpose of DLT assessment.

In general, missing data will not be imputed and only observed values will be analyzed except for the data mentioned below.

If the date of diagnosis on the cancer diagnosis CRF page is partially missing, it will be imputed using the following rules for the purpose of calculating “Time Since Initial Diagnosis” summary.

- If only the day part is missing, day 15 will be used for imputation
- If both day and month parts are missing, July 1st will be used for imputation

If the relationship of an AE record is missing the AE will be considered “Related” to the study treatment for reporting purpose. If the Common Terminology Criteria for Adverse Events (CTCAE) grade of an AE is missing every effort should be made to acquire the information from the investigator. Grade 3 will be assigned to a missing grade for reporting purposes.

In general, missing or partial dates will not be imputed except for AE or medication start and end date.

The general imputation rules of partial missing date for both AE and concomitant medication are detailed below:

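### Subjects who die, progress or stop for toxicity before 75% of a cycle appear in no planned efficacy estimate, although OS, PFS and TTP are timed from Cycle 1 Day 1

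*SAP*

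**What the plan says.** SAP 8.2 defines a population that "includes all enrolled subjects who satisfy all of the following conditions". The first condition is measurable disease with a baseline assessment. The second, in the default definition (a), is "Received at least 75% of 1 cycle of study medication". The third is a post-baseline disease assessment or, failing that, stopping treatment for an adverse event, progression or death. The third condition excuses a missing scan; it does not excuse the dosing threshold. SAP 12.1 says that Cycle 1 compliance feeds this definition.

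SAP 11 applies the set to all efficacy analyses unless stated otherwise. In SAP 16, Tables 6 and 7 assign every efficacy table and figure (best overall response with ORR and DCR, target lesion change, both versions of TTP, PFS, OS) to the Response population. SAP 11.2 to 11.4 start TTP, PFS and OS at Cycle 1 Day 1. Protocol 3.8.2 allows expansion subjects who are not response-evaluable to be replaced until 20 evaluable subjects are reached.

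The protocol is not uniform. Section 11.1.2 has the 75% rule and applies it to early failures too. Section 9.3 says instead that subjects with measurable disease who "receive at least one cycle of SRA737 and have a baseline plus at least 1 post-baseline assessment of disease will be evaluable for response". It then says, with no dosing threshold in that sentence, that subjects with clear progression but no formal assessment and "those without a formal disease assessment before study withdrawal will be considered non-responders". Section 11.2.3 puts all efficacy endpoints on the Response Evaluable Population, and later says that OS and PFS will include data from all subjects.

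**The concern.** Membership of the set depends on what happens after the clock starts. For OS and PFS this removes the earliest deaths from both the risk set and the event count. For ORR and DCR it takes early failures out of the denominator instead of counting them as failures, and replacement can then bring a cohort back to 20 with no trace in the estimate.

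ORR, DCR, TTP, PFS and OS are all listed as primary endpoints (Protocol 3.1.1, SAP 4.1). The trial is single-arm and its efficacy analysis is descriptive, so there is no comparison in which the selection might cancel: the estimates are the result. They would be read as describing subjects who start SRA737, when they describe those who stayed on it long enough to qualify.

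**Working it through.** **Where the threshold falls.** On continuous daily dosing, 0.75 × 28 = 21 days. Protocol 5.2 also allows other schedules. With 5 days on and 2 off there are 20 planned doses in 28 days; 0.75 × 20 = 15, and the 15th dose falls on day 19. With 1 week on and 3 off there are 7 planned doses; 0.75 × 7 = 5.25, so the 6th dose, on day 6, would suffice. Both alternative figures assume that compliance counts planned doses. SAP 12.1 takes compliance from the CRF, whose calculation is not shown; the SAP's formula with a divisor of 28 is only the fallback.

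**Which time-to-event endpoints are exposed.**
- OS: every death before the threshold is lost.
- PFS: early deaths are lost. Early survivors without a scan matter less, because SAP Table 4 would censor them at Cycle 1 Day 1 even if they were included.
- TTP including clinical progression: subjects judged at medical review to have progressed clinically when they stopped before the threshold are lost.
- RECIST-only TTP: little affected. Only radiographic progression counts, and routine scans start at 8 weeks.

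No figure is offered for the shift in OS or PFS, because it depends on when the excluded subjects die or progress, which the documents do not show.

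**ORR and DCR: the plan's own figures first.** Protocol 11.2.3 tabulates Wilson 95% intervals for n = 20. With z = 1.96, the centre is (p + z²/2n)/(1 + z²/n) and the half-width is z√(p(1−p)/n + z²/4n²)/(1 + z²/n). For 3/20 the centre is 0.206 and the half-width 0.154, giving 0.052 to 0.360. For 10/20 the interval is 0.299 to 0.701. For 0/20 the upper limit is 0.161. All 21 rows reproduce to three decimals, so the table is not in dispute.

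**Adding early failures back.** Assume k subjects excluded per 20 evaluable, with k = 2 or 7. The excluded share of those treated is k/(20 + k): 2/22 = 9.1% and 7/27 = 25.9%. This range is an assumption. Its upper end is pessimistic given entry at WHO performance status 0–1 and life expectancy of at least 12 weeks.

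If none of the excluded has response or disease control:

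| | Evaluable set | k = 2 | k = 7 |
|---|---|---|---|
| DCR | 10/20 = 50.0% (29.9–70.1) | 10/22 = 45.5% (26.9–65.3) | 10/27 = 37.0% (21.5–55.8) |
| ORR | 3/20 = 15.0% (5.2–36.0) | 3/22 = 13.6% (4.7–33.3) | 3/27 = 11.1% (3.9–28.1) |

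**Sensitivity.** Let r be the share of the excluded with disease control; then DCR = (10 + kr)/(20 + k).
- r = 0.25: 10.5/22 = 47.7% and 11.75/27 = 43.5%.
- r = 0.5: 11/22 and 13.5/27, both 50.0%, so no bias.

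Let d be the number of responders among the excluded; then ORR = (3 + d)/(20 + k).
- d = 1, k = 7: 4/27 = 14.8%, almost no bias.
- d = 1, k = 2: 4/22 = 18.2%, bias reversed.

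Such cases are possible if the threshold refers to Cycle 1, as SAP 12.1 indicates: a subject whose Cycle 1 dosing is interrupted (Protocol Table 2 allows delays of up to 4 weeks) and who later responds is also left out.

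**The case against.** The strongest reply is that this set is the protocol's own. The synopsis and Protocol 11.1.2 prespecify the 75% rule and apply it explicitly to early progression, toxicity and death; Protocol 11.2.3 puts all efficacy on it; and SAP 8.2 labels definition (a) as the protocol's. Following it is not a departure that SAP 13 had to declare. That stands as to origin. It does not remove the selection, and it does not settle the contrary wording in Protocol 9.3 and 11.2.3.

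It is also fair that the losses are not hidden altogether. SAP 10.1 and Table 14.1.4 give exclusions with reasons, and deaths are listed for all subjects. But no efficacy estimate includes these subjects. The assumed ORR shift (1.4 to 3.9 points) is small beside a 3/20 interval about 31 points wide; imprecision, however, does not excuse an avoidable bias.

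Some stronger readings are not supported:
- That the all-subjects wording for OS and PFS flatly contradicts the Response Evaluable rule. The OS sentence goes straight on to censoring, so it may describe only that.
- That SAP 9.2.3 bars early withdrawals from reporting. It says they "will be included in the reporting if they meet the definition of the analysis population", which is an inclusion rule, and treated subjects meet the safety population.
- That the SAP has no place for Protocol 9.3's early progression or early death ("Death during the first 28 days of treatment"). PD is a response category, deaths are listed, and neither term is an endpoint.
- That all the time-to-event endpoints suffer equally, or that the cut-off is always near three weeks. The working shows otherwise.
- That the SAP's alternative definition (b) is part of this fault. It does not restore early failures, but it is optional, exploratory, separately labelled and declared in SAP 13.

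**Conclusion.** The concern holds and should be fixed. Carried out as written, the plan gives efficacy estimates for subjects selected on treatment received after time zero, and no estimate for all who started. This is clearest for OS, for deaths within PFS, and for TTP including clinical progression. For ORR and DCR the missing piece is an estimate that counts early failures. Separately, Protocol 9.3, 11.1.2 and 11.2.3 need reconciling, and SAP 13 does not do it.

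The existence of the selection follows from the text. Its size does not. The falls of 4.5 to 13.0 points in DCR and 1.4 to 3.9 points in ORR rest on an assumed 2 to 7 exclusions per 20 evaluable and no benefit among them. The denominator of 20 is also illustrative: SAP 9.2.1 reports by tumor type, pooling escalation with expansion and both HGSOC cohorts. A reader might infer that the bias can only be upward. It is probably upward, but it can vanish or reverse if excluded subjects later respond or have disease control, and ORR has no upward bias if there are no responders.

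**What to change.** 1. Analyse OS, PFS and both versions of TTP on all subjects with a Cycle 1 Day 1 dose, a count that SAP 10.1 already produces, by the tumor-type columns of SAP Table 1. List subjects who had only the PK dose separately.
2. Add ORR and DCR on the same Cycle 1 Day 1 set, restricted to subjects with measurable disease and a baseline assessment. Count those with no post-baseline assessment as non-responders without disease control. State that mCRPC subjects eligible on PSA or CTC alone are outside this RECIST rate. Keep definition (a) as a supportive analysis.
3. Reconcile Protocol 9.3, 11.1.2 and 11.2.3 with SAP 8.2, say whether the all-subjects wording for OS and PFS sets the population or only the censoring, and record the decision in SAP 13.

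The cost is SAP wording, one analysis flag and a few extra tables, all from data already collected. The downside is probably slightly less favourable figures, and a conservative count for subjects who stopped for reasons unrelated to efficacy.

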### **8.3. Pharmacokinetics Evaluable Population**

All subjects who receive at least 1 dose of SRA737 and provide at least 1 evaluable PK concentration will be included in the PK analysis. Plasma concentration data will be eligible for inclusion into PK analyses if the subject receives the full dose and does not vomit within 4-hours postdose. Because the endpoints using this population are not reported in the SAP this population will not be included in the ADaM datasets.

### **8.4. Pharmacokinetics/Corrected QT Interval Evaluable Population**

All enrolled subjects who receive at least 1 dose of SRA737 and for whom adequate QTc and ECG data are available will be evaluable for PK/QTc analyses. Because the endpoints using this population are not reported in the SAP this population will not be included in the ADaM datasets.

### **8.5. Pharmacodynamics Evaluable Population**

All enrolled subjects who receive at least 1 dose of SRA737 who have evaluable data for each specific PDn assessment will be evaluable for PDn. Because the endpoints using this population are not reported in the SAP this population will not be included in the ADaM datasets.

## 9. GENERAL CONSIDERATIONS FOR STATISTICAL ANALYSIS

### 9.1. General Principles for Data Analysis

#### 9.1.1. Multicenter Study

The summaries and analyses will be conducted by pooling data from all study centers. If it is identified that a site has disproportionate number of protocol deviations additional summaries excluding the site in question might be carried out.

#### 9.1.2. Testing Strategy and Multiplicity Adjustments

No formal multiplicity adjustment will be performed. All statistical results such as p-values and confidence interval (CI) are supportive in nature.

#### 9.1.3. Examination of Subgroups

Efficacy analyses based on the subgroups defined by tumor type and genetic criteria may be carried out. Additional subgroups might be added if identified during the course of the trial.

## 9.2. General Data Handling Conventions

#### 9.2.1. Data Displays for Reporting

For tables and figures the data will be displayed as shown in the following tables. Any abbreviation used in the column text will be displayed in full description text in the footnote of the output.

Unless specified otherwise all tables will have corresponding listings supporting the table summaries. The default ordering of the listings is by disease categories, site ID, subject ID, test or parameter name (if applicable), sequence number (AE, medical history, or medication), date of event or date of collection (if applicable).

For study population and efficacy, the columns will be grouped by the primary tumor type regardless if a subject was enrolled under escalation or expansion stage.

**Table 1: Data Display for Study Population and Efficacy**

Column Text Display	Description Verbatim terms included in the grouping (including misspelling and specific terms present in the clinical data)	Display Order
CRC	Metastatic Colorectal Cancer Metastatic colorectal Metastatic Colorectal Carcinoma With Abdomial* Mass Colorectal Adenocarcinoma	1
HGSOC	High Grade Serous Ovarian Cancer Platinum resistant ovarian Carcinosarcoma Of Ovary – CCNE1 Amplification: No High grade serous ovarian cancer Platinum-Resistant High Grade Papillary Serous Carcinoma Of The Ovary Serous Adenocarcinoma Peritoneum/Ovary	2
NSCLC	Advanced Non-small cell Lung Cancer Advanced non small cell lung	3
mCRPC	Metastatic Castration-Resistant Prostate Cancer Metastatic castration resistant* prostate Prostate Adenocarcinoma Adenocarcinoma of Prostate	4
HNSCC/SCCA	Head and Neck Squamous Cell Carcinoma Head and neck squamous cell	5
	Squamous cell carcinoma of the anus	
Other	Disease types not included in the previous columns	6
Overall	All subjects in the population	7

\* Misspelling are present in the clinical database and will be kept verbatim for programming purposes

For safety summaries, the columns will be group based on Cycle 1 Day 1 total dose level. For subjects without Day 1 treatment they will be included in the “<=800mg” column.

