4.2 SUBJECT SELECTION CRITERIA

The subject must fulfil the eligibility criteria (listed in Sections 4.2.1 and Section 4.2.2).

4.2.1 *INCLUSION CRITERIA*

Dose Escalation Phase and Cohort Expansion Phase

1. Written (signed and dated) informed consent and capable of co-operating with treatment and follow up.
- 2a. For subjects in the Dose Escalation Phase: any locally advanced or metastatic, histologically or cytologically proven solid tumor or NHL, that is relapsed after or progressing despite conventional treatment for which no conventional therapy is considered appropriate by the investigator or is declined by the subject.
- 2b. For subjects in the Cohort Expansion Phase: locally advanced or metastatic, histologically or cytologically proven malignancy of the types specified in inclusion criterion 10, for which no other conventional therapy is considered appropriate by the investigator or has been declined by the subject.
3. Life expectancy of at least 12 weeks.
4. World Health Organization (WHO) performance status of 0–1 (Appendix 1).
5. Hematological and biochemical indices within the ranges shown below, measured within one week prior to the subject receiving their first dose of investigational medicinal product (IMP).

Laboratory Test	Lower acceptable limit
Hemoglobin (Hb)	≥ 90 g/L
Absolute neutrophil count	$\geq 1.5 \times 10^9$ /L
Platelet count	$\geq 100 \times 10^9$ /L
Bilirubin	$\leq 1.5 \times$ upper limit of normal (ULN) unless due to Gilbert's syndrome in which case up to $3 \times$ ULN is permissible
Alanine aminotransferase and/or aspartate aminotransferase and Alkaline Phosphatase	$\leq 2.5 \times$ ULN unless raised due to tumor in which case up to $5 \times$ ULN is permissible
Serum Creatinine	$\leq 1.5 \times$ ULN

6. Attained the age of 18 years at the time consent is given.
7. Subjects must have archival tumor tissue available for tumor profiling or accessible tumor and willingness to consent to a biopsy for the collection of tumor tissue. Refer to Section 7.1.1 for more details.

Cohort Expansion Phase

8. Subjects must have measurable disease (per Response Evaluation Criteria in Solid Tumors, version 1.1 [RECIST v1.1]) or, for mCRPC, evaluable disease per any of the following:
 - a. Measurable disease per RECIST v1.1;
 - b. Increasing prostate specific antigen (PSA, see PCWG – Appendix 7); or
 - c. Circulating tumor cell (CTC) count of 5 or more cells per 7.5ml of blood.

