9. Subjects must have tumor tissue or ctDNA evidence that their tumor harbors a combination of mutations which are expected to confer sensitivity to Chk1 inhibition. Eligibility will be determined by the Sponsor's review of genetic abnormalities detected in genes in the following categories, as listed in Appendix 6:
 - a. Key tumor suppressor genes regulating G1 cell cycle progression/arrest such as *RB1*, *TP53*, etc. For patients with NHSCC or SCCA, positive HPV status is also considered for eligibility.
 - b. The DDR pathway including *ATM*, *BRCA1*, and *BRCA2*. For patients with CRC, MMR genetic alterations and/or high microsatellite instability are also considered for eligibility.
 - c. Genetic indicators of replicative stress such as gain of function/amplification of *Chk1* or *ATR* or other related gene.
 - d. Oncogenic drivers such as *MYC*, *KRAS*, etc.
 - e. *CCNE1* gene amplification (or alternative genetic alteration with similar functional effect) is required for the *CCNE1* gene amplification-specific HGSOC cohort.
10. Subjects must meet one of the following criteria (a-e):

- a. **Metastatic CRC, defined by the following:**
 - Histologically and/or cytologically confirmed CRC, and
 - Must have received at least 1 prior regimen for advanced/metastatic disease
- b. **HGSOC, defined by the following:**
 - Histologically confirmed high-grade serous ovarian, fallopian tube or primary peritoneal cancer, and
 - Recurrent platinum-intolerant subjects, or those with platinum-resistant disease, defined as radiological evidence of disease progression within 6 months of the last receipt of platinum-based chemotherapy. Patients with platinum refractory disease (ESMO – Appendix 7) are not eligible
- c. **Advanced NSCLC, defined by the following:**
 - Locally advanced and recurrent or metastatic, histologically confirmed NSCLC, and
 - Must have received at least 1 prior regimen for advanced/metastatic disease
- d. **mCRPC, defined by the following:**
 - Histologically or cytologically confirmed adenocarcinoma of the prostate that has progressed after androgen deprivation therapy
- e. **HNSCC or SCCA, defined by the following:**
 - Histologically confirmed HNSCC from any primary site, or SCCA:
 - For HNSCC: locally advanced disease (ie, persistent or progressive disease following curative-intent radiation, and not a candidate for surgical salvage due to incurability or morbidity), or metastatic disease

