## 2. STUDY OBJECTIVES

### 2.1. Primary Objective

- To establish the safety profile of SRA737
- To determine the maximum tolerated dose (MTD) with 1 or more schedules of administration of SRA737
- To propose a recommended Phase 2 dose and schedule of SRA737
- To evaluate the preliminary efficacy of SRA737 including efficacy in prospectively-selected genetically-defined subjects enrolled into indication-specific expansion cohorts

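### SAP Table 1 counts ovarian carcinosarcoma in the HGSOC efficacy column, and no committed response table is limited to subjects who met the expansion criteria

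*SAP*

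**What the plan says.** Part of the primary objective in SAP Section 2.1 is "efficacy in prospectively-selected genetically-defined subjects enrolled into indication-specific expansion cohorts". For study population and efficacy displays, SAP Section 9.2.1 states that "the columns will be grouped by the primary tumor type regardless if a subject was enrolled under escalation or expansion stage". Table 1 then lists the diagnosis terms that make up each column and says that they include specific terms found in the clinical data.

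- **HGSOC column:** one entry is "Carcinosarcoma Of Ovary – CCNE1 Amplification: No".
- **mCRPC column:** beside terms that name castration resistance, it lists two that do not (run together in the text as extracted): "Prostate Adenocarcinoma Adenocarcinoma of Prostate".
- **Other column:** described as "Disease types not included in the previous columns".

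The protocol defines the indications in Section 4.2.1. Criterion 10b asks for "Histologically confirmed high-grade serous ovarian, fallopian tube or primary peritoneal cancer", together with platinum-intolerant or platinum-resistant disease. Criterion 10d asks for "Histologically or cytologically confirmed adenocarcinoma of the prostate that has progressed after androgen deprivation therapy". Criterion 10 applies to the Cohort Expansion Phase. Escalation subjects enter under criterion 2a, which accepts "any locally advanced or metastatic, histologically or cytologically proven solid tumor or NHL" that has relapsed or progressed despite conventional treatment. Under protocol Section 3.6, an escalation subject counts toward an indication cohort only if that subject meets the expansion eligibility criteria.

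**The concern.** The SAP replaces an eligibility test with a text match. Under protocol Section 3.6, criterion 10 decides whether an escalation subject belongs to an indication. Under SAP Table 1, the wording of the diagnosis field decides. For at least one term the two rules disagree: carcinosarcoma of the ovary is not the histology that criterion 10b names, yet it is placed under HGSOC although the Other column is available.

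SAP Section 9.2.1 also requires abbreviations to be written out in the output footnote. The tables would therefore carry the full high-grade serous label over a group that contains another histology.

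Protocol Section 2.6 says that prospective selection is meant to inform which indications are taken forward. The HGSOC rationale in protocol Section 2.2.2 is specific to that disease: TP53 mutation in 96% of profiled samples and CCNE1 amplification in about 20% of patients. ORR, DCR, TTP, PFS and OS under the HGSOC heading should describe that disease, or say where they do not.

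**Working it through.** **1. Terms set against criteria**

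| Table 1 entry | Column | Protocol requirement | What the term shows |
|---|---|---|---|
| Carcinosarcoma of the ovary, CCNE1 not amplified | HGSOC | 10b: high-grade serous histology | A different histology: off-criterion |
| Platinum-resistant ovarian | HGSOC | 10b | Fits the platinum part of 10b; silent on histology and grade |
| Serous adenocarcinoma, peritoneum/ovary | HGSOC | 10b | Fits the serous part and the site; silent on grade |
| Two prostate adenocarcinoma terms | mCRPC | 10d: prostate adenocarcinoma progressed after androgen deprivation | The required histology; silent on progression and metastasis |

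The extracted table has lost its line breaks, so the boundaries between ovarian terms are uncertain. The carcinosarcoma term is in the HGSOC cell either way.

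**2. Does another step in the SAP apply criterion 10?**

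- Section 8.2 (Response Evaluable Population) adds a genetic condition for inclusion in expansion cohorts, but no check of histology or disease state.
- Section 9.1.3 makes subgroups by tumor type and genetic criteria optional.
- Section 16.1, Table 6 lists one best-overall-response table and no version limited to subjects who met the expansion criteria. Protocol Section 11.2.3 had planned ORR and DCR for subjects enrolled in the indication-specific expansions.
- Section 13 says that the disease-type summaries are adapted to actual enrollment and refers to Section 9.2.1. It does not say that a histology outside criterion 10b counts within an indication.

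No committed step repairs the mapping.

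**3. The plan's own figure**

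Protocol Section 11.2.3 gives Wilson limits of 0.052 to 0.360 for 3/20. With p = 0.15, n = 20, z = 1.96 and z² = 3.8415:

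- Denominator: 1 + z²/n = 1.1921
- Centre: (0.15 + 3.8415/40)/1.1921 = 0.2064
- Half-width: 1.96 × √(0.1275/20 + 3.8415/1600)/1.1921 = 0.1540
- Limits: 0.0524 and 0.3604, as stated. The other 20 rows of that table also reproduce.

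**4. Largest effect of one subject**

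Remove one subject from k/n:

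- If a responder: k/n − (k−1)/(n−1) = (n−k)/[n(n−1)], a fall.
- If a non-responder: k/(n−1) − k/n = k/[n(n−1)], a rise.

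At n = 20 the divisor is 380, so the largest change is 19/380 = 5.0 points. At n = 40 it is 1560, so the largest change is 39/1560 = 2.5 points. The value 40 is an assumption: Table 1 has a single HGSOC column, and the protocol plans two HGSOC cohorts of about 20.

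**5. Examples (responder counts assumed)**

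| With the subject | Without, if a responder | Without, if a non-responder |
|---|---|---|
| 3/20 = 15.0% (5.2 to 36.0%) | 2/19 = 10.5% (2.9 to 31.4%) | 3/19 = 15.8% (5.5 to 37.6%) |
| 6/40 = 15.0% | 5/39 = 12.8% | 6/39 = 15.4% |
| 0/20 = 0% (upper limit 16.1%) | not applicable | 0/19 = 0% (upper limit 16.8%) |

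The interval for 3/20 is 36.0 − 5.2 = 30.8 points wide, far more than the shift from one subject.

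**The case against.** The strongest reply has four parts.

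**The columns are described as tumor type, and the regrouping is disclosed.** SAP Section 9.2.1 does not present them as criterion-10 cohorts, Section 13 refers to the regrouping, every term is printed, and Section 9.1.2 calls the statistical results supportive. This lowers the stakes. It does not explain why a different histology sits under a heading that names high-grade serous disease rather than ovarian cancer.

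**Silence in a diagnosis term is not ineligibility.** A reader might infer that the two prostate terms bring in men who are not castration-resistant, or that the ovarian terms without a grade bring in low-grade disease. The documents do not support that. Criterion 10d uses the same prostate histology. Criterion 2a also requires relapse or progression despite conventional treatment, and protocol Section 2.2.3 treats androgen deprivation as standard therapy. Platinum resistance is itself part of criterion 10b, which also covers primary peritoneal cancer. Protocol Section 2.2.2 puts the high-grade share of papillary serous tumors at 90%. This part of the reply stands: escalation entry makes non-qualifying subjects possible, not shown.

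**The carcinosarcoma subject may have been enrolled in an HGSOC cohort.** The entry records CCNE1 status, the attribute that separates the two HGSOC cohorts, and protocol Section 4 requires the sponsor to confirm the cohort. This is an inference, since the stage is not stated. If it is right, dropping an enrolled cohort member after data exist in an open-label trial would be a problem of its own. The fix has to allow for this.

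**A strict documentation rule can misclassify in the other direction.** Sending every subject with incomplete text to Other would remove true HGSOC and mCRPC cases. This also stands, and it argues for an added display rather than rebuilt columns.

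**Conclusion.** The point holds in a limited form. One Table 1 term, carcinosarcoma of the ovary, is demonstrably outside criterion 10b and is counted as HGSOC. More generally, the SAP assigns subjects to indications without the eligibility condition that protocol Section 3.6 sets for escalation subjects, and it commits to no response table that restores it. For the mCRPC column and the remaining ovarian terms, the most that can be said is that they may include escalation subjects who do not meet criterion 10.

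The effect is small and can go either way: at most 5 points for one subject at n = 20, or 2.5 points at n = 40, against an interval about 31 points wide at 3/20. These figures assume the planned cohort sizes and one affected subject who is in the Response Evaluable Population. The documents give neither the number of affected subjects nor their evaluability or response. Table 1's statement that its terms come from the clinical data suggests at least one carcinosarcoma subject. If that subject is not response evaluable, the efficacy tables do not change.

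A reader might go further and conclude that the HGSOC and mCRPC results are both materially contaminated. The documents do not support that conclusion.

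**What to change.** 1. In SAP Table 1, move the carcinosarcoma term to Other. If that subject was enrolled in an HGSOC expansion cohort, keep the subject in the column, name the histology in a footnote, and show the HGSOC result with and without the subject.
2. Keep the other tumor-type columns as they are.
3. Add to SAP Table 6 a committed ORR and DCR display by indication, limited to subjects who met the expansion criteria (criteria 9 and 10).
4. Derive the flag for that display from eligibility records, including the sponsor's cohort confirmation required by protocol Section 4, and from prior-therapy records (already listed in Listing 16.2.1.5). Set it without reference to response.
5. State the mapping and the added display in SAP Section 13.

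The cost is one derived flag, one extra table, possibly a footnote, and slightly smaller denominators in the restricted display. No new data collection is needed if the eligibility records are available for the analysis.
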